## TIME AND EVENTS SCHEDULE

### Cohort 1 (Groups 1-3) and Cohorts 2a and 2b (Groups 1-2)

Group	Screening Phase a (≤8 weeks)	Vaccination Phase and Post-vaccination Phase b									Long-term Follow-up Phase b,c	
		D1	D2-D7	D8	-	D29	D30-D35	D36	D50	D71 d	D209	D365
					D15	D57	D58-D63	D64	D78	D99 d	D237	
					D15	D85	D86-D91	D92	D106	D127 d	D265	
Study procedures		Prime		+7d pp	+14d pp	Boost		+7d pb	+21d pb	+42d pb	+6m pb e	+1y pp
Screening/Administrative												
Informed consent/assent f		X										
Inclusion/exclusion criteria		X g										
Medical history and demographics		X										
Prestudy therapies h		X										
Serum pregnancy test i		X										
HIV-1/2 serology (Cohorts 1 and 2b only)		X										
Follicle-stimulating hormone (FSH) j		X										
Test of Understanding (TOU) f		X										
Check clinical status + available data			X k									
Randomization			X									
Study Vaccine Administration l		▲				▼						
Safety Assessments												
Urine Pregnancy test i			X m				X m					
Electrocardiogram (ECG) n	X											
Physical examination o	X	X m		X		X m		X	X	X	X	X
Vital signs p	X	X m				X m						
Distribution of subject diary		X				X						
Completion of diary at home q			X				X					
Review of diary by site staff				X				X				
Adverse events r					Continuous							
Serious adverse events and immediate reportable events s					Continuous							
Concomitant medications	X	X	X	X	X t	X	X	X	X	X	X u	X u

Group	Screening Phase a (≤8 weeks)	Vaccination Phase and Post-vaccination Phase b									Long-term Follow-up Phase b,c	
		D1	D2-D7	D8	-	D29	D30-D35	D36	D50	D71 d	D209	D365
Group 1 (Cohorts 1, 2a, 2b)		D15	D57		D58-D63	D64	D78	D99 d	D237			
Group 2 (Cohorts 1, 2a, 2b)		D15	D85		D86-D91	D92	D106	D127 d	D265			
Group 3 (Cohort 1 only)												
Study procedures		Prime		+7d pp	+14d pp	Boost		+7d pb	+21d pb	+42d pb	+6m pb e	+1y pp
Clinical Laboratory Assessments												
Chemistry, hematology (10 mL) v	X	X m		X		X m		X				

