### **9.1.3. Vaccination Phase (Prime and Boost)**

If eligible, the subject will come for the baseline visit (Day 1). The investigator should ensure that all enrollment criteria have been met during screening. If a subject's clinical status changes (including available laboratory results or receipt of additional medical records) after screening but before the prime vaccination (Day 1) such that the subject no longer meets all enrollment criteria, then the subject should be excluded from further participation in the study. If the initial laboratory sampling occurred more than 8 weeks before baseline (Day 1), sampling will need to be repeated.

Eligible subjects will be allocated (by central randomization) to a vaccination schedule as described in Section 5.

The subjects will be vaccinated as described in Section 6, with prime vaccinations administered at Day 1 for all groups, and boost vaccinations at Day 29 (Group 1), Day 57 (Group 2) or Day 85 (Group 3) unless any of the pre-specified criteria not to proceed with vaccination are met (refer to Sections 6.2, 6.3 and 10.2 for details) or if a pause for vaccination of further subjects has been installed (see Section 9.3.2).

Before each vaccination (prime and boost), a urine pregnancy test (for female subjects of childbearing potential), a targeted physical examination and measurements of vital signs will be performed and blood will be drawn for safety and immunogenicity assessments. Refer to Section 9.4 for further details on the immunogenicity evaluations.

Study vaccine will be prepared on-site by unblinded qualified study-site personnel not involved in any other study-related procedure who will place a blinding tape on the syringe to mask its content and send the vaccine to a blinded study vaccine administrator (see [Definitions of Terms](#)) for administration to the subject (see Section 14.3 for details). Refer to Section 6 for further details on dosage and administration and post-vaccination monitoring.

All adverse events, serious adverse events, IREs and pregnancies will be collected and documented on the CRF, together with the information on any concomitant medications. For reporting of IREs, refer to Section 12.3.3.

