Regimen*	Post-dose 1	Date and time of Dose 1 administration	Minimum of: a) 23:59 on the date of last contact (for early study discontinuations) b) 23:59 on the date of relative Day 29 Post-dose 1 c) one minute prior to Dose 2 administration d) 23:59 on the date of database cut-off (in case of interim analysis)
Post-dose 1 FU		One minute after the end of the Post-dose 1 period	Minimum of: a) 23:59 on the date of last contact (for early study discontinuation or completion) b) one minute prior to Dose 2 administration c) 23:59 on the date of database cut-off (in case of interim analysis)
Regimen*	Post-dose 2	Date and time of Dose 2 administration	Minimum of: a) 23:59 on the date of last contact (for early study discontinuation or completion) b) 23:59 on the date of relative Day 29 Post-dose 2 c) 23:59 on the date of database cut-off (in case of interim analysis) Note: subjects who do not receive Dose 2 will not have a Post-dose 2 period.
Post-dose 2 FU		One minute after the end of the Post-dose 2 period	Minimum of: a) 23:59 on the date of database cut-off (in case of interim analysis) b) 23:59 on the date of last contact (for early study discontinuation or completion)
Regimen*	Post-dose 3	Date and time of Dose 3 administration	Minimum of: a) 23:59 on the date of last contact (for early study discontinuation or completion) b) 23:59 on the date of relative Day 29 Post-dose 3 c) 23:59 on the date of database cut-off (in case of interim analysis) Note: subjects who do not receive Dose 3 will not have a Post-dose 3 period.

Post-dose 3 FU		One minute after the end of the Post-dose 3 period	Minimum of: a) 23:59 on the date of database cut-off (in case of interim analysis) b) 23:59 on the date of last contact (for early study discontinuation or completion)
-------------------	--	--	---

Note 1: * Regimen period includes both the Post-dose 1, Post-dose 2 and Post-dose 3 periods.

Note 2: FU = follow-up.

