7.2.1. Definitions

In determining toxicity grades, the following rules will be applied:

- Worst grades/abnormalities are determined over the entire period (eg, Post-dose 1, Post-dose 2 or Post-dose 3) separately, including all post-baseline measurements of the corresponding period.
- The abnormalities “abnormally low” and “abnormally high” are considered equally important and both abnormalities are shown in the tables. (This means that the sum of the percentages can exceed 100%).
- If a laboratory value falls within the grading as specified in the grading table but also within the local laboratory normal limits, the value is considered as normal or Grade 0.
- Laboratory results falling between the grading scales will be allocated to the adjacent worst-case grade (because the scale for some parameters in the grading table is not continuous as there may be zones where toxicity grade definitions do not exist).

An abnormality (toxicity grade or abnormality based on normal ranges) will be considered as following vaccination in a period and/or phase if it is worse than the corresponding baseline record. If the baseline value is missing, the abnormality is always considered as following vaccination. A shift from “abnormally low” at baseline to “abnormally high” post-baseline (or vice versa) is also considered as an abnormality following vaccination.

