7.2.3. Analysis Methods

Laboratory abnormalities (except CD4+ cell counts in HIV-infected subjects) will be determined in accordance with the toxicity grading tables (Attachment 3 and Attachment 4), and in accordance with the normal ranges of the clinical laboratory. The worst abnormalities following vaccination will be summarized (ie, showing number and percentage) by regimen and presented per period/phase, with special attention to Grade 3 toxicities. Focus will be on clinical abnormalities that occur during Post-dose 1, Post-dose 2 and Post-dose 3 periods, as well as the Regimen Phase. Similar tables for worst abnormalities will be provided pooled by vaccine (dose). A listing will also be provided for subjects with any abnormal laboratory findings following vaccination. For CD4+ cell counts in HIV-infected subjects, a listing will also be generated.

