- In addition to the date information, time information is considered to allocate AEs to periods, if available.

- The imputation of missing end dates of ongoing AEs will only be used to derive the duration of the event (ie, to give an indication of the minimum duration). The imputed end dates will not be shown in the data listings.

Step 2: Combination of events:

Overlapping/consecutive events are defined as events of the same subject with the same preferred term which have at least 1 day overlap or for which the start date of an event is 1 day after the end date of the preceding event. Overlapping/consecutive events may be combined into one AE or not, according to the following rules:

- 1) If overlapping/consecutive events start in a non-active phase (Screening or any of Post-dose FU phases) followed by an AE in an active (Post-dose 1 or Post-dose 2) period, they are allocated to their respective periods/phases and are considered as separate events.
- 2) In case overlapping/consecutive events start within a single period/phase, they are considered as one and the same AE. The individual events which contribute to this AE are retained as individual records in the Analysis Data Model (ADaM) database but are assigned the same onset, period/phase, and total duration.
- 3) In case overlapping/consecutive events start in an active period followed by a non-active phase, they are allocated only to the active period and are considered as one and the same AE. The individual events which contribute to this AE are retained as individual records in the ADaM database but are assigned the same onset, period, and total duration.
- 4) In case an active period is followed by another active period, and the overlapping/consecutive events start in both periods, they are allocated to their respective period and are considered as separate AEs. The same rule applies for 2 non-active phases.

- Remarks:
 1. Time is not considered when determining overlap of events.
 2. Events can only be combined into one and the same AE if their start and stop dates are known.
 3. In case the completely missing end date is imputed (for calculation of duration), this date is also considered as a complete date.

Examples:

Screening phase: start date: 14JUN2016 - stop date: 28JUN2016

Post-dose 1 period: start date: 28JUN2016 - stop date: 26JUL2016

Post-dose 1 FU phase: start date: 27JUL2016 - stop date: 15AUG2016

Example for the above Scenario 1

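### The pre-boost laboratory sample counts in Post-dose 1 and the Regimen phase for Group 1 subjects boosted by Day 29 but not for on-schedule Groups 2 and 3, so worst-grade percentages are not comparable between schedules

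*SAP*

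**What the plan says.** SAP 2.1 assigns laboratory abnormalities (CD4+ counts apart) to the Table 2 periods rather than to visits. Post-dose 1 starts at Dose 1 and ends at the earliest of last contact, the data cut-off and "23:59 on the date of relative Day 29 Post-dose 1 c) one minute prior to Dose 2 administration". Anything after that and before Dose 2 belongs to Post-dose 1 FU, which starts "One minute after the end of the Post-dose 1 period". The note under Table 2 says that the "Regimen period includes both the Post-dose 1, Post-dose 2 and Post-dose 3 periods", so the FU phases are outside it.

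SAP 7.2.1 states: "Worst grades/abnormalities are determined over the entire period (eg, Post-dose 1, Post-dose 2 or Post-dose 3) separately, including all post-baseline measurements". An abnormality counts as following vaccination if it is worse than the pre-prime baseline. SAP 7.2.3 reports numbers and percentages by regimen and per period or phase, and adds: "Focus will be on clinical abnormalities that occur during Post-dose 1, Post-dose 2 and Post-dose 3 periods, as well as the Regimen Phase".

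In the protocol, Section 9.1.3 says that before each vaccination "blood will be drawn for safety and immunogenicity assessments". The Time and Events Schedule row "Chemistry, hematology (10 mL") marks screening, Day 1, Day 8, the boost day before dosing, and 7 days post-boost. The Cohort 3 schedule has the same pattern. Protocol Table 3 sets the boost at Day 29, 57 or 85, each ±3 days.

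**The concern.** The cut-off for Post-dose 1 is the target boost day of Group 1. A sample that the protocol schedules in every group is therefore counted in the main laboratory columns for one schedule and moved to a follow-up phase for the others. Under a worst-grade rule, an extra sample can only raise the percentage or leave it unchanged.

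Up to the boost, the groups have received the same prime at the same dose, so their Post-dose 1 laboratory percentages should agree apart from chance. Under the planned rule they are not expected to. Protocol Section 11 says that the primary analysis is meant to help judge which schedule is the best candidate. A reader who compares schedules in the Post-dose 1 or Regimen laboratory tables could take a sampling artefact for a tolerability difference. The SAP plans no by-visit summary of chemistry and hematology that would show the cause.

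**Working it through.** **1. Which visits carry a laboratory draw.** The protocol's cumulative blood volumes give a check. Without PBMC, Cohort 1 is stated to reach 110 mL (Group 1) and 120 mL (Groups 2 and 3) by Day 365.
- Laboratory draws: screening, Day 1, Day 8, boost, 7 days post-boost = 5 × 10 = 50 mL.
- Serum, Group 1: Day 1, boost, 7 and 21 days post-boost, 6 months post-boost, Day 365 = 6 × 10 = 60 mL. Total 110 mL.
- Serum, Groups 2 and 3: the same plus Day 15 = 7 × 10 = 70 mL. Total 120 mL.

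Both totals match. Every group has a pre-boost laboratory draw, and the extra Day 15 visit has none, so that visit does not offset the difference.

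**2. Day count.** The example in SAP Attachment 1 reads "Post-dose 1 period: start date: 28JUN2016 - stop date: 26JUL2016". With 28 June as Day 1, 26 July is Day 29. A sample drawn before a Day 29 boost is therefore inside Post-dose 1.

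**3. Scheduled post-prime laboratory samples by period, for each in-window boost day.**

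| Group and boost day | Post-dose 1 | Post-dose 2 | Regimen (no third dose) |
|---|---|---|---|
| Group 1, Days 26–29 | 2 | 1 | 3 |
| Group 1, Days 30–32 | 1 | 1 | 2 |
| Group 2, Days 54–60 | 1 | 1 | 2 |
| Group 3, Days 82–88 | 1 | 1 | 2 |

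Boosts postponed under Protocol 6.2 (up to 10 days beyond the window) or delayed past the window by the study pause also leave the pre-boost sample in FU.

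**4. Effect on the Post-dose 1 percentage.** The inputs in this step are assumptions, not figures from the documents. Let p be the probability that one sample shows an abnormality worse than baseline, ρ the within-subject correlation between the two samples, and f the fraction of Group 1 boosted by Day 29.
- One sample: p.
- Two samples: p + p(1 − p)(1 − ρ).
- Group 1 overall: p + f·p(1 − p)(1 − ρ).

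For f, 4/7 is the share of Days 26–32 that lie on or before Day 29, as if boosts were spread evenly over the window.

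At p = 5%, p(1 − p) = 0.0475:
- f = 1, ρ = 0: 0.05 + 0.0475 = 9.75%.
- f = 1, ρ = 0.5: 0.05 + 0.0475 × 0.5 = 7.4%.
- f = 4/7, ρ = 0: 0.05 + 4/7 × 0.0475 = 7.7%.
- f = 4/7, ρ = 0.5: 0.05 + 4/7 × 0.0475 × 0.5 = 6.4%.
- Groups 2 and 3: 5%.

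With 220 vaccinees in Group 1 of Cohort 1, this is about 14 (220 × 0.064) to 21 (220 × 0.0975) subjects with an abnormality. In Group 2, also 220 vaccinees, it is 11.

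| p (Groups 2 and 3) | Group 1, f = 4/7, ρ = 0.5 | Group 1, f = 1, ρ = 0 |
|---|---|---|
| 1% | 1.3% | 2.0% |
| 5% | 6.4% | 9.75% |
| 10% | 12.6% | 19.0% |
| 20% | 24.6% | 36.0% |

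The difference vanishes only if ρ = 1 or f = 0.

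**5. Regimen phase.** With independent samples and full capture at p = 5%: 1 − 0.95³ = 14.3% in Group 1, against 1 − 0.95² = 9.75% in Groups 2 and 3.

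**The case against.** A common 28-day window after each dose is a normal convention and equalises time at risk. A Day 29 sample lies inside it; Day 57 and Day 85 samples do not. That argument works for adverse events, which are collected continuously. It does not work for tests done at a few fixed visits, where the number of looks inside the window decides the result.

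Post-dose 2, the period after the only component that differs between schedules, has one scheduled sample in every group. A Group 1 excess confined to Post-dose 1 would be hard to read as an effect of the boost interval. This stands for Post-dose 2, but the Regimen column carries the imbalance too.

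Placebo is randomized 5:1 within each group, so an excess due to sampling should appear in both arms. This stands: the contrast within a schedule is unbiased, and the placebo column gives an attentive reader a warning.

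No formal test is planned, the primary endpoints are adverse events rather than laboratory tables, and clinically relevant worsening is also analysed as adverse events (SAP 7.2). This limits the consequence. The percentages by schedule are nevertheless what a descriptive analysis delivers.

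The FU phase may be tabulated as well, since results are given per period or phase. Even so, the same scheduled sample would sit in different columns by group and stay out of the Regimen phase for Groups 2 and 3.

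The two samples may not be equally informative. All samples share one baseline, which makes them positively correlated. Protocol 1.1.2.1 describes the most frequent Phase 1 laboratory events as transient, so the later sample may have a lower rate than Day 8. Both points shrink the gap; neither reverses it.

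**Conclusion.** The point holds for two sets of numbers: worst-grade laboratory percentages by schedule in Post-dose 1 and in the Regimen phase. The direction follows from the rules alone: Group 1 is expected to be higher unless the two samples always agree or nobody is boosted by Day 29. The size cannot be fixed from the documents. At an assumed 5% per sample, the scenarios worked through give about 6.4% to 9.75% in Group 1 against 5%. These take the same rate at both samples, correlation 0 to 0.5, and 4/7 to full capture. Higher correlation or lower capture would bring Group 1 closer to 5%.

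A reader might infer more than this:
- That Group 1 rates will roughly double. This needs independent samples and every boost given by Day 29; the protocol allows boosts to Day 32 and beyond.
- That all of the planned Group 1 subjects (264 + 3 × 66 = 462) are affected. Only those with a pre-boost sample by Day 29 are.
- That the vaccine looks less safe against placebo, or that the post-boost comparison is distorted. Sampling is the same in both arms of a schedule, and Post-dose 2 is balanced.
- That the choice of schedule is compromised. No test rests on these tables, and they are one part of a descriptive safety assessment.

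The issue is worth correcting because it is predictable, the SAP does not adjust for it, and the correction needs no new data.

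**What to change.** Adopt one of two changes in SAP 2.1 and 7.2.1.

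1. Base the by-schedule laboratory tables for Post-dose 1 and the Regimen phase on samples common to all groups. The scheduled pre-boost sample goes in its own column for every schedule. Post-dose 1 then rests on the Day 8 sample, and the Regimen phase on Day 8 plus 7 days post-boost, with any unscheduled samples in the period.
2. Keep Table 2 as it is and add a by-visit worst-grade table (Day 8, pre-boost, 7 days post-boost) by schedule and by vaccine or placebo. Name that table as the one for comparing schedules.

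Under either option, note that the pre-boost column lies about 28, 56 and 84 days after the prime, so it is not one time point since vaccination.

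The cost is SAP wording and one extra column or table. Under option 1, a Group 1 abnormality first seen before the boost leaves the Post-dose 1 column and appears in the pre-boost column; if clinically relevant, it is still analysed as an adverse event. Option 2 removes nothing from the planned tables, but the unequal columns remain and need a footnote giving the scheduled samples per period.

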2.1. Analysis Visit Windows and Periods

Because subjects do not always adhere to the protocol visit schedule, the following rules will be applied to assign actual visits (immunogenicity assessments) to analysis visits. The analysis visit windows and target days for each visit are displayed in

[Table 1](#). The reference day will be defined as:

- Day of first (Dose 1) vaccination if the actual visit occurs prior to the second (Dose 2) vaccination.
- Day of second (Dose 2) vaccination if the actual visit occurs after the second vaccination but prior to the third (Dose 3: only for subjects in the substudy) vaccination.

- Day of third (Dose 3: only for subjects in the substudy) vaccination if the actual visit occurs after the third vaccination.

Only the analysis time points and assays that are in scope for a specific statistical analysis (e.g. Interim Analysis, Final Analysis) are to be considered when assigning assessments to analysis visit windows. If a subject has 2 or more assessments within the same interval (analysis visit window), the one closest to the target day will be used for generating tables with descriptive statistics and graphical displays presenting data per time point. If 2 assessments are equidistant from the target day within the same interval, the latest assessment will be used. All assignments will be made in chronological order.

Because the analysis of adverse events (AEs) and laboratory abnormalities (except CD4+ cell counts in HIV-infected subjects) will be presented per period (and not per time point), these will be assigned to the analysis period and/or phase based on [Table 2](#). For CD4+ cell counts, the electronic case report form (eCRF) visit schedules will be used for the post baseline assessments. If only unscheduled visits are present for a time point, then the one closest to the scheduled visit will be used. If distances of multiple assessments to the scheduled visit are equal, the measurement with the latest date will be used. Similar to the CD4+ cell counts, the eCRF visits will also be used to present vital signs data of Cohort 3 subjects per time point.

Table 1: Analysis Visit Windows

Time Interval (Label on Output)	Time Interval PP ^a (Day)	Time Interval IG ^b (Day)	Target Time Point (Day)
Prior to Second (Dose 2) Vaccination			
Day 1 (Baseline)	≤ 1	≤ 1	1
Day 15 (14 days Post-dose 1)	[13; 17]	[2; 21]	15
Day 29 (28 days Post-dose 1)	[26; 32]	[22; 42]	29
Day 57 (56 days Post-dose 1)	[54; 60]	[43; 70]	57

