1. PERIOD ALLOCATION OF ADVERSE EVENTS

Solicited events will always be allocated to the Post-dose 1 or Post-dose 2 period, as appropriate.

Unsolicited AEs will be allocated to the different periods per the following rules:

Step 1: Allocation of unsolicited events to the periods/phases:

The AEs present in the database are allocated to periods/phases based on their start date/time. If the start date/time of an event falls between (or on) the start and stop date/time of a period/phase, the AE is attributed to that period/phase (ie, AEs following vaccination).

Incomplete dates (ie, time and/or day and/or month and/or year missing):

- 1) In case of partial start or stop dates, the events are allocated to the periods/phases using the available partial information on start and end date; no imputation will be done. If, for instance, for the AE start date only month and year are available, these data are compared to the month and year information of the periods/phases. This rule may lead to multiplication of the event because of its assignment to multiple periods/phases (see below example).
- 2) In case of a completely missing start date, the event will be allocated to the appropriate period/phase (eg, Post-dose 1 or Post-dose 2) and consequently the Regimen period; except if the end date of the AE falls before the start of the Post-dose 1 or Post-dose 2 period.
- 3) In case of a completely missing end date (ie, only for the calculation of duration):
 - In case the AE is flagged as ongoing the date is imputed by the cut-off date of the analysis for subjects still ongoing in the study, and by the end date of the last period/phase for subjects who discontinued or completed the trial.
 - In case the AE is not flagged as ongoing, the end date is considered as unknown, and the date will remain missing.

Examples:

Screening Phase: start date: 14JUN2016 - stop date: 28JUN2016

Post-dose 1 period: start date: 28JUN2016 - stop date: 19JUL2016

1) Adverse event: start date: JUN2016- stop date: 15JUL2016

As the start date only has information about month and year, only this information will be used from the periods/phases (ie, assuming any day of Jun is possible) and therefore the AE will be assigned to the Screening Phase as well as to the Post-dose 1 period.

2) Adverse event: start date: JUL2016- stop date 14JUL2016

As the AE starts after the Screening Phase and after the start of the Post-dose 1 period, it is only assigned to the Post-dose 1 period.

Remarks:

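### SAP Table 2 does not end Post-dose 2 follow-up at Dose 3, so in the Cohort 1 substudy that phase overlaps Post-dose 3 and Post-dose 3 follow-up

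*SAP*

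**What the plan says.** SAP Section 2.1, Table 2 defines a phase or period around each dose. Post-dose 2 ends at the latest on relative Day 29. Post-dose 2 FU then starts "One minute after the end of the Post-dose 2 period", and its stop rule is "Minimum of: a) 23:59 on the date of database cut-off (in case of interim analysis) b) 23:59 on the date of last contact". The list has only those two items. The Post-dose 1 FU row has a further item: "b) one minute prior to Dose 2 administration". Post-dose 3 starts at Dose 3 and ends at the latest on relative Day 29. Post-dose 3 FU then runs to the same last contact or cut-off.

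Three other rules bear on this:

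- **Allocation of AEs.** Attachment 1, Step 1 says that if an unsolicited event's start "falls between (or on) the start and stop date/time of a period/phase, the AE is attributed to that period/phase".
- **Allocation of laboratory data.** Section 2.1 says that AEs and laboratory abnormalities (CD4+ counts excepted) "will be presented per period (and not per time point), these will be assigned to the analysis period and/or phase based on" Table 2.
- **Combining events.** Attachment 1, Step 2 covers overlapping or consecutive events with the same preferred term. Rule 1 keeps them separate when they start in a non-active phase "followed by an AE in an active (Post-dose 1 or Post-dose 2) period". Rule 2 says: "In case overlapping/consecutive events start within a single period/phase, they are considered as one and the same AE". The records are then given one onset, one period or phase and one duration.

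**The concern.** A phase meant to hold follow-up after two doses also takes in what happens after the third. No SAP text gives the later phase priority when an event with a complete start date falls in two phases; assignment to several phases is acknowledged only for incomplete dates. SAP 7.1.3 and 7.2.3 present AE and laboratory summaries per period/phase. Wherever Post-dose 2 FU is shown, a post-Dose 3 event would also read as two-dose follow-up.

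Step 2 could do more than add a second flag. Its rule 1 was not extended to Post-dose 3, so it does not clearly protect an event starting after Dose 3 from being merged with one starting before. That matters because AEs in the 28 days after the third vaccination are part of a secondary safety endpoint (Protocol 11.1.2).

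**Working it through.** **Inputs.** Boost is on Day 29 (Group 1) or Day 57 (Group 2). Dose 3 is 12 to 15 months post prime, taken as study Day 365 to 456. The 6-month visit after Dose 3 is Day 180 ±15 and the 1-year visit is Day 365 ±30 (Protocol Table 6). Substudy size is about 90; Groups 1 and 2 have 264 planned subjects each (Protocol Table 1). The day of dosing is relative Day 1. Last contact is taken as the 1-year visit.

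**Subjects affected.** 90 / (2 × 264) = 90/528 = 17%.

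**Overlap at the final analysis.** Take Group 1 with Dose 3 on study Day 365.

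- Post-dose 2: Days 29 to 57. Post-dose 2 FU: from Day 58 to last contact.
- Last contact: 365 + 364 = Day 729.
- Post-dose 3: Days 365 to 393, which is 29 days, all inside Post-dose 2 FU.
- Post-dose 3 FU: Days 394 to 729, which is 336 days, all inside Post-dose 2 FU.
- Total overlap: 29 + 336 = 365 days. With the ±30-day window: 29 + 306 = 335 to 29 + 366 = 395 days.

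The total is the same for Group 2 and for Dose 3 on Day 456. It counts calendar days including the day of Dose 3; elapsed time gives one day less.

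**Overlap at the substudy interim.** The last subject to reach the 6-month visit has about 180 days (165 to 195). Subjects dosed earlier have more.

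**Other rows.** Post-dose 2 also lacks a Dose 3 stop, without effect. Even a Group 2 boost at Day 57 + 3 + 10 ends that period on 57 + 3 + 10 + 28 = Day 98, long before Dose 3.

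**Step 1 applied to test events** (Group 1, Dose 3 on Day 365):

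| Start | As written | With a stop before Dose 3 |
|---|---|---|
| Unsolicited AE, Day 368 | Post-dose 2 FU and Post-dose 3 | Post-dose 3 |
| Laboratory sample, Day 372 (Day 8 post Dose 3) | Post-dose 2 FU and Post-dose 3 | Post-dose 3 |
| SAE, Day 465 | Post-dose 2 FU and Post-dose 3 FU | Post-dose 3 FU |

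The error adds events to Post-dose 2 FU and removes none from any other period. Regimen is built from the three post-dose periods, so it does not change either.

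**Step 2 applied to a constructed pair.** AE1 starts on Day 360 and is still present at Dose 3, so it is recorded (SAP Section 7). AE2, same preferred term, starts on Day 368 while AE1 continues.

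1. As written, both starts lie in Post-dose 2 FU.
2. Rule 1 does not apply literally, because AE2 starts in Post-dose 3 and the bracket names only Post-dose 1 and Post-dose 2.
3. Rule 2 does apply literally: both start within a single phase. Both records take the Day 360 onset and Post-dose 2 FU.
4. AE2 can then drop out of Post-dose 3, and with it out of Regimen.
5. With the Table 2 stop and Post-dose 3 added to rule 1, rule 2 no longer fits, and rule 1 keeps AE2 in Post-dose 3.

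The Table 2 change alone ends the merge under rule 2 but leaves this pair without a rule that names it, so both edits are needed.

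**The case against.** The strongest reply is that this is a drafting slip with an obvious intent. The Post-dose 1 FU row shows the convention, and a programmer would probably apply it. SAP 7.1 summarizes AEs in the three vaccination periods; Sections 7 and 7.2.3 focus on those periods and Regimen. No table of Post-dose 2 FU is named. Listings carry all AEs whatever their phase. Days of overlap are not an effect size, since the SAP reports numbers and percentages of subjects and no person-time rates. All of this stands and is why the point is minor. It does not remove the defect: the cut is not written, and per period/phase presentation does not exclude the follow-up phases.

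On Step 2, the reply is that rule 1 already covers events beginning in any follow-up phase, and that SAP 7.1 counts Post-dose 3 as a vaccination period, so keeping such events separate is the natural reading. It is also a narrow case. It needs same-term events that overlap or are consecutive, with known dates. Between 42 days post boost and Dose 3 only SAEs and IREs are collected, apart from events still present at Dose 3. The narrowness stands. The natural reading, however, requires a period to be read into a bracket that omits it.

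A reader might also infer that solicited reactions after Dose 3 have no home, because Attachment 1 says "Solicited events will always be allocated to the Post-dose 1 or Post-dose 2 period, as appropriate". The documents do not support that. SAP 7.1.2 sends solicited events to the Section 2.1 periods, and 7.1.3 defines time to onset from Post-dose 3 as well.

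**Conclusion.** The rule is wrong as written, and the point is minor. In about 90 substudy subjects, unsolicited AEs and laboratory abnormalities starting after Dose 3 are allocated to two phases. Phase flags and any output showing Post-dose 2 FU would be wrong. After 28 days post Dose 3 only SAEs and IREs are collected, and the only scheduled post-Dose 3 chemistry and hematology draw is on Day 8, so the number of doubly flagged records is limited. No event rate is given in the documents and none is assumed here.

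Two stronger readings do not hold. The first is that Post-dose 3 or entire-period results are generally miscounted: under Step 1 alone they are unchanged, and loss from Post-dose 3 can arise only through the Step 2 merge, whose frequency is unknown and probably low. The second is that a year of overlap affects every analysis. It applies to subjects who complete the substudy, at the final analysis; the overlap is shorter at the 6-month substudy interim for subjects not yet at their last visit, and absent wherever the cut-off precedes Dose 3. The day counts assume that last contact is the 1-year visit and that the subject does not discontinue earlier.

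**What to change.** 1. In SAP Table 2, add a third item to the list of end points for Post-dose 2 FU, stopping the phase one minute before Dose 3 is given, as the Post-dose 1 FU row does for Dose 2. The same stop rule can stay as it is for Post-dose 3 FU, where no later dose exists.
2. In Attachment 1, Step 2, rule 1, add Post-dose 3 to the active periods in the bracket.
3. For consistency with SAP 7.1.2, add Post-dose 3 to the solicited-event sentence at the head of Attachment 1.

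With the first change the overlap is 0 days in every scenario checked. The cost is one line in Table 2, two wording corrections and the matching derivation in the analysis programs. No new data are needed.
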